Study Title: A Single arm, Multicenter, Prospective, Clinical Study on a Novel Minimally Invasive Posterior Sacroiliac Fusion Device: **SECURE STUDY**

Principal Investigator:

[name]

Medical Monitors

[name]
[name]

Version date: April 4, 2022

Sponsor: PainTEQ

Version date: 04 April 2022

Principal Investigator: [name]

Medical Monitors: [name] and [name].

Study Title: A Single arm, Multicenter, Prospective, Clinical Study on a Novel Minimally Invasive Posterior Sacroiliac Fusion Device: **SECURE STUDY**

Co- Investigator(s): up to 10 sites

Table of Contents

I. Purpose, Background and Rationale	3
II. Research Plan and Design	3
III. Subject Participation	8
IV. Data Collection and Protection	9
V. Data Analysis and Reporting	9
VI	13
Bibliography / References	13

I. Purpose, Background and Rationale

The purpose of this post-market study is to evaluate data and evidence on the safety and efficacy of utilizing the LinQ system for sacroiliac disease. SI fusion has been a long-standing treatment for refractory SI joint disease that has failed conservative treatment. SI joint disease accounts for approximately 30-40% of all low back pain according to a recently published literature. Recently newer techniques have been developed to treat SI joint dysfunction in a less invasive method. A lateral approach utilizing three triangular titanium implants resulted in a statistically significant improvement in pain and disability when compared to conservative management for SI joint dysfunction. Although this approach is less invasive than a true open approach, it still carries significant risk and invasiveness. Risk of laterally placed screws into the spinal canal poses risk of neurological compromise. Non-weight bearing status, incisional pain, and recovery time are significant factors that must be acceptable to the clinician and patient.

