Recently, an FDA approved posteriorly placed allograft into the mid-portion of the SI joint has shown significant promise as an alternative option to traditional or lateral SI fusion. The LinQ system is a minimally invasive, percutaneous, single incision technique for SI fusion. Utilizing a posterior approach eliminates the risk of spinal canal compromises and improves the overall safety profile. Additionally, using a single incision and avoiding screws reduces invasiveness and significantly reduces recovery times. A recent abstract presented by Pyles on 20 consecutive patients showed an average 83% reduction in pain at 3 months with no serious adverse effects or complications using the LinQ system[3]. The purpose of this multicenter, prospective, clinical series is to further establish the data, efficacy, and safety on the LinQ system for chronic Sacroiliac Joint Disease.

II. Research Plan and Design

A. Study Objectives:

The purpose of this post-market study is to gather evidence documenting the performance and clinical outcomes associated with treatment of sacroiliac disease with the LinQ fusion procedure.

B. Study Type and Design

Multicenter Center, Prospective, Single arm Clinical study

C. Sample size, statistical methods, and power calculation:

Anticipated study enrollment will be ongoing patients for registry.

Power calculation based on paired T test, Alpha 0.05, Beta 0.2, Power 0.8, Effect Size 0.5, two sided yielded sample size of 34 patients. Assuming a 20 percent loss to follow up or study exit rate, fifty patients would be sufficient to achieve study aims.

Statistical methods would include paired T tests for quantitative measures which include VAS score, Oswestry Disability Index, and Promis-29.

D. Subject Criteria:

Inclusion criteria:

- Age 21-70
- Patient has lower back pain for >6 months inadequately responsive to conservative care
- Patient has at least 3 of 4 physical examination maneuvers specific for the SI joint (FABER, Gaenslen test, Stork/Gillete, and Yoman)
- Patient has improvement in lower back pain numeric rating scale (NRS) of at least 50% after injection of local anesthetic into affected SI joint(s) with confirmed arthrogram, within 30-60 min from injection
- Degenerative sacroiliitis as SIJ mediated in the context of either radiographic evidence of SIJ degeneration, evident on computed tomography or Xrays or a history of prior lumbar fusion.

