 - Underlying diagnosis: degenerative sacroiliitis/sacroiliac joint disruption
 - Prior lumbar fusion (y/n)
 - Prior treatments (PT, FA, SIJ injection)

1. Timeline: Patients included in the study return for follow-up visits at 7-14 days, 1, 3 months, 6, 12, 18, and 24months post-treatment. Primary endpoint will be 6 month time point.
2. No randomization as treatment with the LinQ system will be performed regardless of whether the patient agrees to be in the research.

F. Risk/benefit assessment:

As appropriate, address the following parameters as each relates to the individual subject in the study.

1. Psychological risk: minimal, less than 1%
2. Social risk minimal, less than 1%
3. Potential benefit of participating in the study
 - a. To the individual subject and/or parent if any:

Improvement in the following domains:

 - a. Pain
 - b. Physical functioning
 - c. Emotional functioning
 - d. Patient global rating of improvement and satisfaction
 - e. Symptoms and adverse events
 - f. Patient disposition
 - b. To the population from which the subject is drawn: The study will provide

evidence to support a new treatment modality that is safe and effective. This

treatment modality also does not require repetition or multiple treatments unlike other treatments for sacroiliac joint dysfunction. It will also offer a salvage therapeutic option for patients who have failed other treatment modalities.

- c. To science, society, and humanity in general: Advancement of minimally invasive musculoskeletal techniques that may significantly reduce associated morbidity, mortality, and overall cost of treatment for chronic musculoskeletal related pain.

G. Location where study will be performed: Multisite

H. Collaboration: Multisite

I. Single IRB Review for a Multi-site study:

IRB local approval

J. Personnel who will conduct the study, including:

- 1. Indicate, by title, who will be present during study procedure(s): Study coordinator, attending physician, company representative, fellow physician (when available).
- 2. Primary responsibility for the following activities, for example:
 - a. Determining eligibility: PI, study attendings, senior trainees
 - b. Obtaining informed consent: Attendings at the study site including co-investigators, senior trainees at study site, and/or research coordinators
 - c. Providing on-going information to the study sponsor and the IRB: No Study Sponsors
 - d. Maintaining participant's research records: Research coordinator

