B. Procedures to protect subject confidentiality:

Patient identifiers may be included in master spreadsheet for reference to clinical chart if need arises for further review. Data will be de-identified with master spreadsheet containing patient identifiers linked to generated ID. A secondary spreadsheet will be generated containing pertinent study measures linked to the generated ID. The study coordinator will serve as the honest broker or buffer between master and secondary spreadsheets.

V. Data Analysis and Reporting

A. Statistical and Data Analysis:

Statistical analysis will include paired t-test of quantitative measures such as VAS pain score, Oswestry Disability Index, PROMIS 29, and quantitative secondary outcomes. ANOVA regression analysis will be performed to identify potential correlates of improved outcomes measures and adverse outcomes. IBM SPSS Statistics will be utilized to perform the analysis. Interim analysis will be performed on an anticipated monthly basis by a statistician. At no time will identifying information be transferred.

B. Outcome Measures:

i. Primary Outcome Measures

1. Binary success failure composite end point. A subject was considered a success if all of the following criteria were met
 - a. Reduction from baseline VAS SIJ pain by at least 20 mm
 - b. Absence of device related serious adverse events,
 - c. Absence of neurologic worsening related to the lumbosacral nerve roots,
 - d. Absence of surgical reintervention (removal, revision reoperation or supplemental fixation) for SIJ pain

ii. Secondary Outcome Measures

1. Improvement in baseline in VAS from baseline at 6 months
2. Oswestry Disability Index at 6 months follow up
3. PROMIS-29 at 6 months follow up
4. Patient Satisfaction with PGIC
5. Morphine milligram equivalent usage at all time points

C. Study results to participants:

Once final analysis completed, debriefing report will be given at follow up appointment or via telephone call. If no further contact maintained, copy of published manuscript will be sent to patients. Purpose of this will be to debrief patients as to study results.

D. Visit Schedule

	At least 7 days prior to Baseline	(within 4 weeks of surgery)									
Informed Consent	X										
Inclusion / Exclusion Review	X	X									
Urine Pregnancy test (if required)	X										
Surgery Information			X								
VAS	X	X		X	X	X	X	X	X	X	
PROMIS-29		X		X	X	X	X	X	X	X	
ODI	X	x		X	X	X	X	X	X	X	
Patient Satisfaction					X	X	X	X	X	X	

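### The stated tests of treatment effect are paired t-tests of change from baseline in a single-arm study; they cannot carry the protocol's promise of evidence that the treatment is effective

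*Protocol*

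**What the plan says.** - **Design.** Section II.B: "Multicenter Center, Prospective, Single arm Clinical study". Section II.E, item 2: "No randomization as treatment with the LinQ system will be performed regardless of whether the patient agrees to be in the research". There is no concurrent or historical comparator, and patients know what they received.
- **Tests of effect.** Section II.C names paired t-tests for VAS, ODI and PROMIS-29. Section V.A repeats this: "Statistical analysis will include paired t-test of quantitative measures such as VAS pain score, Oswestry Disability Index, PROMIS 29, and quantitative secondary outcomes". V.A also names ANOVA regression, but only to look for correlates of outcome.
- **Sample size.** Section II.C: "Power calculation based on paired T test, Alpha 0.05, Beta 0.2, Power 0.8, Effect Size 0.5, two sided yielded sample size of 34 patients", followed by "Assuming a 20 percent loss to follow up or study exit rate, fifty patients would be sufficient to achieve study aims". The aims are thus tied to the paired t-test.
- **Claim.** Section I gives the purpose as evaluating safety and efficacy. Section II.F item 3b says the study will provide "evidence to support a new treatment modality that is safe and effective". Section II.A is milder and speaks of documenting performance and clinical outcomes.
- **Primary endpoint.** Section V.B.i defines a binary composite whose first criterion is "Reduction from baseline VAS SIJ pain by at least 20 mm". The other three criteria are absence of device-related serious adverse events, of neurologic worsening and of surgical reintervention. Section II.E puts the primary endpoint at 6 months. The composite plays no part in the sample size.

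**The concern.** The null hypothesis of a paired t-test is a mean change of exactly zero. In an uncontrolled, unblinded study with self-reported outcomes, zero change is not the state in which the device does nothing. Entry requires a VAS of at least 50 mm and an ODI of at least 30% (section II.D), so some regression to the mean is expected. Natural course, expectation after a procedure and concurrent care can add to it. A significant t-test shows that patients changed, not why.

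The test is also detached from the protocol's own standard of success, a 20 mm fall in the individual patient plus three safety conditions. A mean change can be clearly different from zero while most patients miss that standard. If the effectiveness wording in II.F were rested on these tests, the conclusion would go beyond what the design can show. Section I itself supports a different device, the lateral implants, by "improvement in pain and disability when compared to conservative management for SI joint dysfunction"; nothing in this study's stated tests makes a comparison of that kind.

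**Working it through.** **Inputs from the protocol.** Two-sided alpha 0.05, power 0.80, effect size 0.5, n = 34, 20% loss, 50 enrolled (II.C); entry VAS of at least 50 mm (II.D); 20 mm criterion (V.B.i).

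**Assumed, not in the documents.** SD of VAS change 20, 25 or 30 mm; normal changes; mean non-device fall 5, 10 or 15 mm.

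**1. The plan's own figure.** Power comes from the noncentral t distribution with n − 1 degrees of freedom and noncentrality 0.5 × √n. n = 33 gives 0.795 and n = 34 gives 0.808, so 34 is reproduced. Allowing for 20% loss, 34 / 0.80 = 42.5, rounded up to 43; 50 is above that and leaves 50 × 0.80 = 40 completers.

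**2. Smallest observed mean fall that is significant at n = 40.** t(0.975, 39) / √40 = 0.320 SD. At SD 20, 25 and 30 mm this is 6.4, 8.0 and 9.6 mm, about a third to a half of 20 mm.

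**3. Probability of significance with zero device effect, n = 40.** Noncentrality = (non-device fall / SD) × √40.

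| Non-device fall | SD 20 | SD 25 | SD 30 |
|---|---|---|---|
| 0 mm | 5% | 5% | 5% |
| 5 mm | 34% | 23% | 18% |
| 10 mm | 87% | 69% | 54% |
| 15 mm | 99.6% | 96% | 87% |

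**4. Regression to the mean from the VAS entry cut alone.** Assume a population SD s = 20 mm, population mean μ of 50 to 65 mm and test-retest correlation ρ of 0.5 to 0.8. With a = (50 − μ)/s and λ = φ(a)/(1 − Φ(a)), the expected fall is s(1 − ρ)λ.
- μ = 50, ρ = 0.5: a = 0, λ = 0.798, fall 20 × 0.5 × 0.798 = 8.0 mm; SD of change 18.3 mm; significant in 77% of trials.
- μ = 65, ρ = 0.8: a = −0.75, λ = 0.389, fall 20 × 0.2 × 0.389 = 1.6 mm; SD of change 12.4 mm; significant in 12%.

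**5. The design effect against the 20 mm criterion.** 0.5 SD is 10 mm at SD 20 and 15 mm at SD 30. The share of patients falling by at least 20 mm is 1 − Φ((20 − mean)/SD).
- SD 20: 1 − Φ(10/20) = 31%.
- SD 30: 1 − Φ(5/30) = 43%.

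At 40 completers the t-test has 87% power at this effect, yet most patients would miss the VAS part of the primary endpoint.

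**6. Precision of the composite.** An exact (Clopper-Pearson) 95% CI for 20 successes in 40 runs from 34% to 66%, about plus or minus 16 points.

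**The case against.** The strongest reply is that the protocol nowhere says a significant t-test establishes effectiveness. V.A lists analyses, and not exhaustively. The wording in II.F stands in a potential-benefit entry rather than in an objective or hypothesis. II.A states a descriptive aim. The primary outcome is the composite, so a poor rate of 20 mm responses would be visible. This stands as far as it goes: the protocol contains no explicit rule turning the t-test into a claim. But II.C sizes the study on that test and calls the size enough for the study aims, section I gives efficacy as the purpose, and no other test of treatment effect is stated.

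Several stronger readings are tempting, and the documents do not support them:

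- *The t-tests are the only tests.* ANOVA regression is also named; they are the only stated tests of treatment effect.
- *The t-tests will usually be significant with a useless device.* This depends on a non-device change that the protocol does not give. At 5 mm it happens in 18-34% of trials. Entry requires more than 6 months of pain despite conservative care, and VAS is taken at screening and again at baseline; both bear on how large that change would be.
- *The true type I error exceeds 0.05.* The null of zero change is tested at 5%. The protocol sets no null of being no better than other care.
- *No composite result could count against the device.* A goal for the composite may stand in an SAP that is not shown, so its absence here is not the fault.
- *A single-arm study is unacceptable.* For a post-market study it is acceptable and openly declared. The mismatch is between test and claim.

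**Conclusion.** The point holds as a mismatch between what the stated tests can show and what the protocol says the study will provide. That part rests on the text alone. Its size rests on assumptions about the SD and the non-device change. Over the ranges shown, a non-device improvement of about 10 mm makes significance more likely than not and 15 mm makes it highly likely, while 5 mm does not. Regression to the mean from the entry cut alone may or may not suffice (12-77%). The gap between the 0.5 SD design effect and the 20 mm criterion needs only the assumed SD and normality. This is a matter of wording and of which result leads the report; it does not require a different design.

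**What to change.** 1. In V.A, state that the paired t-tests describe within-patient change and do not by themselves support a conclusion of effectiveness.
2. In V.A, name the 6-month composite success rate with an exact 95% CI as the main result.
3. Reword II.F item 3b and the efficacy purpose in section I to say that the study describes outcomes after treatment, in line with II.A. The stronger wording could stay only if a justified performance goal for the composite is fixed before any outcome data are viewed, including the interim looks that V.A expects monthly.

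The source of a goal needs care. Conservative-management arms of randomised trials are an obvious candidate, but the device-event and reintervention criteria have no direct counterpart in patients without an implant, and the documents do not show whether the cited trials report this composite. Purely as an illustration, with an assumed goal of 50% and 40 completers, at least 27 successes would be needed (exact one-sided alpha 0.019), with 70% power at a true rate of 70%.

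The cost is text only: no extra patients, visits or data. The downside is a more modest claim with a wide interval, about plus or minus 16 points at 40 completers.

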 - e. Completing physical examination: Attendings and trainees at study site
 - f. Taking vital signs, height, weight: Clinic staff
 - g. Drawing / collecting laboratory specimens: Not applicable
 - h. Performing / conducting tests, procedures, interventions, questionnaires: Attending physician and fellow physicians at study site
 - i. Completing study data forms: Research coordinator
 - j. Managing study database: Research coordinator

K. Adverse Event Monitoring

Adverse events and unanticipated problems will be ascertained and handled per standard of care as applies to any procedure. Problems that would be considered serious and reported to the IRB include infection, new skeletal fracture resulting from procedure, unanticipated post-operative admission, and neurologic injury and would be monitored for on an ongoing basis as per standard of care. The reporting timeframe would be within two weeks of incident to allow for appropriate additional diagnostic testing and treatment while maintaining study responsiveness to adverse events.

If patient experiences an adverse event or post-procedural problem, this will be treated per standard of care. This would include standard of care treatment of any related injury and potential device explanation. Patient may opt out of study at any time voluntarily. This would be monitored and discussed on an ongoing basis in the setting of an adverse event or post-procedural problem.

III. Subject Participation

A. Recruitment:

1. Potential study participants will come from the existing patient population of the investigators in each individual practice.

Recruitment can be performed by interventional pain providers and will be offered to anyone who is a candidate for the LinQ fusion procedure and meet the inclusion and exclusion criteria for the study. This research studies the LinQ system, a legally-marketed device, determined by that health care practitioner to be in the best interests of the patient. Patients will undergo treatment with the LinQ fusion procedure regardless of participation in the research. Therefore, the procedures being conducted because of the research are limited to data collection and the use of the LinQ system is not a research procedure.

B. Informed consent process and timing of obtaining of consent

The following study personnel may participate in the consent process: PI, co-Investigators, senior trainees, research assistants, and research coordinator.

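### Section V.A applies *ANOVA regression* to correlates of adverse outcomes, which are rare yes/no events; an exact or penalised method, or plain description, fits them better (minor)

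*Protocol*

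**What the plan says.** Section V.A (Statistical and Data Analysis) gives paired t-tests for the quantitative measures. It then names one method for two kinds of outcome: "ANOVA regression analysis will be performed to identify potential correlates of improved outcomes measures and adverse outcomes". No other method for correlates is named, and none for yes/no outcomes.

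The protocol does not define adverse outcomes, but the safety outcomes that it lists are all events that either occur or do not:

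- Section II.K (Adverse Event Monitoring): "Problems that would be considered serious and reported to the IRB include infection, new skeletal fracture resulting from procedure, unanticipated post-operative admission, and neurologic injury".
- Section V.B.i (Primary Outcome Measures): "Absence of device related serious adverse events" and "Absence of neurologic worsening related to the lumbosacral nerve roots", together with absence of surgical reintervention.

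Section II.C sets the size of the study: "Assuming a 20 percent loss to follow up or study exit rate, fifty patients would be sufficient to achieve study aims". Section I cites one earlier series of 20 patients with this device, in which no serious adverse effect was seen. The candidate correlates are not named. Section II.E lists baseline items recorded as yes/no, among them smoking and prior lumbar fusion, which are natural candidates.

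**The concern.** ANOVA and linear regression assume a quantitative response with roughly constant variance. A rare 0/1 event has neither property: its variance depends on its probability, and a group with no events contributes no variance at all. If a single event falls in a small subgroup, the pooled variance is tiny, the F statistic is large, and the p-value is too small.

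The protocol itself fixes this method, so this is not detail left to a SAP. A SAP that followed V.A would inherit the mismatch, and one that did not would contradict the protocol. Safety is a stated purpose of the study and publication is planned, so one chance event could be published as a statistically significant predictor of harm.

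The concern does not extend to the paired t-tests, to ANOVA for quantitative change, or to the primary composite.

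**Working it through.** **Inputs from the protocol.** Planned enrolment is 50 with 20% loss (II.C), so 50 × 0.8 = 40 remain. The two-sided alpha is 0.05 (II.C). The cited series had 0 serious events in 20 patients (I).

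**Assumptions.** The protocol gives neither event rates nor subgroup sizes. Rates of 5%, 10% and 20% and every subgroup size from 4 to 20 were used: 3 × 17 = 51 settings.

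**The plan's own figure.** A paired t-test with effect size 0.5, two-sided alpha 0.05 and power 0.80 needs 33.4 patients, so 34. The protocol's figure reproduces. It has no bearing on the correlates analysis.

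**How few events?** From 0 of 20, the one-sided 95% upper limit for the serious event rate is 1 − 0.05^(1/20) = 13.9%, or about 7 events in 50. At a 5% rate the expected number is 2.0 in 40 patients or 2.5 in 50.

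**One event in a subgroup of 8, none in the other 32.**

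- Within-group sum of squares: 8 × 0.125 × 0.875 = 0.875. Pooled variance: 0.875/38 = 0.0230.
- t = 0.125/√(0.0230 × (1/8 + 1/32)) = 2.08 on 38 df, p = 0.044. With two groups the ANOVA F is t².
- Fisher's exact test: p = 8/40 = 0.20.
- Firth logistic regression, likelihood-ratio test: p = 0.095.

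**The same pattern for other subgroup sizes, 40 patients.**

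| Subgroup | ANOVA p | Fisher p | Firth p |
|---|---|---|---|
| 4 | 0.0017 | 0.10 | 0.031 |
| 5 | 0.0064 | 0.125 | 0.044 |
| 6 | 0.015 | 0.15 | 0.059 |
| 7 | 0.028 | 0.175 | 0.076 |
| 8 | 0.044 | 0.20 | 0.095 |
| 9 | 0.063 | 0.225 | 0.116 |

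With 50 patients, ANOVA p is below 0.05 for subgroups of 4 to 10 (0.0004 to 0.044), while Fisher p is 0.08 to 0.20.

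**Conditional error.** If exactly one event occurs and the correlate is irrelevant, the event lies in a subgroup of size m with probability m/40. For m = 4 to 8, ANOVA therefore declares significance in 10% to 20% of such trials.

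**Unconditional error.** Exactly one event is only one of the possible outcomes. At a 5% rate its probability in 40 patients is 40 × 0.05 × 0.95^39 = 0.271, so for m = 8 it contributes 0.271 × 0.20 = 0.054. Other outcomes bring the total to 0.086. Enumerating both binomials over the 51 settings, at nominal 0.05, gives:

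| Method | 40 patients | 50 patients |
|---|---|---|
| ANOVA | 0.012 to 0.086 | 0.016 to 0.078 |
| Fisher | 0.002 to 0.034 | 0.005 to 0.034 |
| Firth | 0.005 to 0.056 | 0.009 to 0.047 |

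ANOVA exceeds 0.06 in 4 of 51 settings with 40 patients (subgroups 6, 7 and 8 at 5%; 8 at 10%) and in 3 of 51 with 50 patients (subgroups 4, 9 and 10 at 5%). At a 20% rate it is 0.032 to 0.056 with 40 patients, which is close to nominal.

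**Why not ordinary logistic regression?** Its estimate is infinite when a group has no events or only events. With 50 patients split 40/10, that happens with probability 90%, 65%, 36% and 11% at event rates of 2%, 5%, 10% and 20%.

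**The case against.** The strongest reply is that the practical harm is small. The single-event illustration is a selected case, and a subgroup of 8 is the largest that gives p below 0.05 with 40 patients. At assumed rates of 2%, 5% and 10%, exactly one event occurs in only about 36%, 27% and 7% of trials of 40. Averaged over the 51 settings, ANOVA's type I error is 0.040 with 40 patients and 0.042 with 50, and it is at or below 0.05 in 41 and 42 of them. At a 2% rate the worst case is much the same: 0.082 with 40 patients and 0.088 with 50. All of this stands, and it is why the point is minor.

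The wording is also ambiguous. *ANOVA regression* is not a defined model, and adverse outcomes could be read to include worsening on VAS, ODI or PROMIS-29, where linear methods fit. That reading is possible, but every safety outcome the protocol itemises is an event, and the ambiguity is itself a reason to reword the sentence.

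The base of 40 can be questioned too. Adverse events are collected from surgery onward, so patients lost later still contribute early events. Results for 50 are therefore given as well, and the conclusion is the same.

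Finally, the alternatives are imperfect. Firth regression still gives p below 0.05 for a single event in subgroups of 4 and 5 with 40 patients, and of 4, 5 and 6 with 50 (0.021, 0.030, 0.041). Fisher's test is conservative and will find little. This stands as well. For very few events, description protects better than any test.

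**Conclusion.** The concern holds, as a minor point. Section V.A fixes a method for quantitative responses and applies it to outcomes that, as the protocol describes them, are yes/no events and probably rare. The harm is specific: one event in a small subgroup (4 to 8 of 40, or 4 to 10 of 50) becomes nominally significant by ANOVA when Fisher's p is 0.08 to 0.20. The overall type I error reaches at most 0.086 in the settings examined at rates of 5% to 20%, and it is near or below nominal in most of them.

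The conclusion rests on reading adverse outcomes as events and on assumed event rates and subgroup sizes. If events were as common as 20%, ANOVA would be acceptable. The sample size and the primary and secondary efficacy conclusions are not affected.

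**What to change.** Replace the sentence in V.A with wording such as:

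> ANOVA or linear regression will be used for correlates of quantitative change. Adverse events and other yes/no outcomes will be analysed with Fisher's exact test or, for adjusted analyses, exact or penalised (Firth) logistic regression. Where only one event of a type occurs, it will be described without a test. The correlates analysis is exploratory.

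This needs a sentence or two and a little programming, with no new data or patients. V.A names IBM SPSS, so the sponsor should confirm that the exact or penalised regression can be run there or name other software. The statistical price is low sensitivity: with so few events, valid methods will identify few correlates.
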